16.4 Adverse Event Reporting

All adverse events and adverse device effects occurring during the clinical trial must be recorded by the investigator on the appropriate AE form in the eCRF, within a reasonable time (up to 5 calendar days from investigator's awareness of the event). All AEs will be characterized by the following criteria:

Doc No: 220CLD

Rev: 03 Date: August 26, 2016

Page 52 of 93

- Intensity or Severity
- Relatedness
- Outcome
- Treatment or Action Taken.

16.4.1 Intensity or Severity

The following categories of the intensity of an adverse event are to be used:

Mild – Awareness of a sign or symptom that does not interfere with the patient's usual activity or is transient, resolved without treatment and with no sequelae.

Moderate – Interferes with the patient's usual activity and/or requires symptomatic treatment.

Severe – Symptom(s) causing severe discomfort and significant impact of the patient's usual activity and requires treatment.

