16.3 Anticipated Adverse Events

The Vibrant Capsule targets pathophysiological parameters of chronic constipation by inducing natural bowel activity without using chemical supplements.

Anticipated Adverse Events include those that are reasonably expected to occur in association with a clinical investigation assessing a treatment for functional constipation. Events can occur as a result of the disease or as a result of the treatment (including usage of the home base unit). They may include but are not limited to the following (in alphabetical order):

- Abdominal pain/discomfort/cramping
- Blood in the stool may develop or increase
- Bloating/Flatulence
- Diarrhea
- Nausea may develop or increase
- Rectal pain may develop or increase
- Sensation of vibration in the abdomen
- Uncontrolled leakage of stool may occur
- Vomiting may develop

All events listed above, and additional events that the investigator will evaluate will fit the definition of 'anticipated event', will be categorized as such in the study.

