16.4.4 Treatment or Action taken

The treatment or action taken after the occurrence of an AE or SAE will be reported as: Interventional Treatment - Surgical, percutaneous or other procedure Medical Treatment - Medication frequency of administration reduction/interruption or discontinuation, or medication initiated for event

None - No action is taken

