17.3.2 Decision Rules

The following decision upon the interim analysis report are planned:

- O Stop the study in case of severe safety concern
- o Continue the study as planned.
- o Modify the frequency of use and/or the device's usability

Doc No: 220CLD

Rev: 03 Date: August 26, 2016

Page 56 of 93

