17.8.7 Safety Analysis

Adverse events (AE) will be presented by seriousness, severity and relation to treatment by treatment group. The number of reports, the number of subjects, and the incidence (percent of subjects) will be tabulated by study arm.

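### The adverse-event intensity scale in section 16.4.1 keeps an intense event judged not to need treatment out of Severe, and lets it be graded Mild if it is also transient and leaves no sequelae

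*Combined protocol and SAP*

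**What the plan says.** Section 16.4.1 gives three grades.

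- Mild opens by referring to the patient's awareness of something; it covers an event that "does not interfere with the patient's usual activity or is transient, resolved without treatment and with no sequelae".
- Moderate is an event that "Interferes with the patient's usual activity and/or requires symptomatic treatment".
- Severe is one or more symptoms "causing severe discomfort and significant impact of the patient's usual activity and requires treatment".

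Nothing in 16.4.1 says which grade to use when two definitions fit.

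Section 16.4 lists intensity, relatedness, outcome, and treatment or action as four separate characteristics of an event. Outcome has its own categories in 16.4.3, which separate recovery with and without sequelae. Section 16.4.4 then begins "The treatment or action taken after the occurrence of an AE or SAE will be reported as", and one of its categories is that no action was taken.

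The grade is used in 17.8.7: "Adverse events (AE) will be presented by seriousness, severity and relation to treatment by treatment group". Section 17.3.1 says that ease of use, tolerability and safety will be assessed at the interim, but defines no measure for them.

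**The concern.** An intensity scale should rank events by how bad they were. This one brings treatment and outcome, which have their own fields, back into the grade. Need for treatment becomes a gate to Severe, and quick untreated recovery becomes a route to Mild whatever the discomfort or loss of activity.

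Safety and tolerability of a new administration frequency are stated objectives (section 12). The study has one arm, so no control group shares the grading error and the severity distribution is read as it stands. Up to 15 centers will grade events. After the first capsule, all others are taken at home, and from the second treatment week section 15.9 plans one call per week. Some events will therefore be graded after they have ended, when it is easy to note that they resolved untreated and harder to say that they required treatment. Abdominal pain or cramping and nausea are among the anticipated events in 16.3, although the documents do not say how often these are intense, brief or untreated.

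**Working it through.** The plan states no figure on this point, so there is nothing to reproduce. The check is logical.

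**Inputs, all from 16.4.1.** Describe an event by five features: interference with usual activity (none, some, significant), severe discomfort (yes/no), transient (yes/no), requires treatment (yes/no), sequelae (yes/no). This gives 3 × 2 × 2 × 2 × 2 = 48 profiles.

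**Definitions as conditions.**
- Severe: severe discomfort AND significant interference AND requires treatment.
- Moderate: any interference OR requires treatment.
- Mild, reading A: no interference, OR (transient AND no treatment AND no sequelae).
- Mild, reading B: (no interference OR transient) AND no treatment AND no sequelae.

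**Profiles with severe discomfort and significant interference** (2 × 2 × 2 = 8):

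| Requires treatment | Transient | Sequelae | Severe | Moderate | Mild (A and B) |
|---|---|---|---|---|---|
| yes | yes or no | yes or no (4 profiles) | fits | fits | no |
| no | no | yes or no (2 profiles) | no | fits | no |
| no | yes | yes (1 profile) | no | fits | no |
| no | yes | no (1 profile) | no | fits | fits |

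Four of the 8 cannot be Severe. All four fit Moderate, and one also fits Mild under either reading.

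**All 48 profiles.** Mild and Moderate overlap in 12 under reading A: 8 with no interference that require treatment, plus 4 with interference that are transient, untreated and without sequelae. Under reading B they overlap in 4, and another 4 (no interference, no treatment, sequelae present) fit no grade. Every Severe profile also fits Moderate.

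**What the second branch of Mild does.** An event that does not interfere with activity already satisfies the first alternative. The only events that the transient alternative can add are ones that do interfere.

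**After the fix set out below.** Mild becomes no interference; Moderate is unchanged; Severe becomes severe discomfort AND significant interference; the highest fitting grade is recorded.
- Severe: 8 profiles.
- Moderate: 32 profiles with interference, less the 8 Severe, plus 8 without interference that require treatment = 32.
- Mild: 8 profiles.
- Total: 8 + 32 + 8 = 48. Each profile has one grade and none is left out.

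**Size, by assumption only.** Let p be the share of 134 subjects with an intense event, and u the share of those judged not to require treatment. The documents give neither. Expected subjects with an event graded Severe = 134 × p × (1 − u).

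| p | All intense (134 × p) | u = 25% | u = 75% |
|---|---|---|---|
| 2% | 2.7 | 2.0 | 0.7 |
| 5% | 6.7 | 5.0 | 1.7 |
| 10% | 13.4 | 10.1 | 3.4 |

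At the interim, one subject of 20 is 1/20 = 5%.

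**The case against.** The strongest reply is that the scale is looser than ideal but that little depends on it.

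- Mild opens with awareness of a sign or symptom, and a patient who cannot carry on usual activity is more than aware. That is a sensible way to grade, and such an event does fit Moderate. But the opening words set no upper limit on intensity, and the transient alternative would do nothing if it covered only events without interference. Mild is permitted, though not forced.
- Section 16.4.4 counts reduced, interrupted or stopped administration as medical treatment. On that usage, an intense cramp that leads a patient to skip capsules has been treated, and the group barred from Severe shrinks. This stands as a limit on size. But 16.4.1 does not refer to 16.4.4, so sites cannot tell whether that usage applies to the grade.
- All events are still recorded and tabulated by seriousness and relation, and abdominal pain and discomfort are also collected daily in the eDiary and analysed as secondary endpoints (17.2.2). This is correct, and it confines the problem to the grade itself.

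A reader might also infer more than the text supports:

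- That brief events cannot be Severe. Severe has no duration condition; a short event that requires treatment qualifies.
- That untreated events cannot be Severe. The condition is that treatment is required, not that it was given.
- That any transient untreated event may be Mild. That branch also needs the absence of sequelae.
- That the final tolerability result is flattered. Section 17.8.4 presents non-completion, non-completion because of adverse events and time to withdrawal; none uses the grade.
- That the interim stopping rule depends on the grade. The wording in 17.3.2, "Stop the study in case of severe safety concern", is not linked to a count of Severe events. SAE status has its own criteria in 16.2, and suspension in section 28 turns on the occurrence of events.

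**Conclusion.** The defect is in the text and does not depend on any assumed rate. Its effect on severity is one-sided: where treatment, transience and outcome change the grade of an intense event, they lower it. The lack of a precedence rule also lets two sites grade the same event differently and both comply.

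The demonstrated reach is the severity presentation in 17.8.7. The interim review in 17.3.1 may be affected too, because it has no defined measure and severity grades are a natural input. The number of events involved cannot be computed from the documents; the table of expected counts only shows how the count would move under assumed values of p and u. This should be corrected because the change is small and the safety description of a single-arm study rests on these tables.

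**What to change.** In 16.4.1:

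1. In Mild, delete "or is transient, resolved without treatment and with no sequelae".
2. In Severe, delete the last three words of the definition, which make treatment a condition.
3. Keep Moderate as written, including need for symptomatic treatment. Without it, an event that needs treatment but does not limit activity would drop to Mild.
4. Add a sentence that, if more than one definition fits, the highest applicable grade is recorded. Significant impact is also interference, so Severe and Moderate will still overlap, and this sentence settles it.

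Treatment and outcome remain in 16.4.3 and 16.4.4, so no information is lost. The cost is the wording of 16.4.1 and the eCRF completion guide. The downside is that the reported number of moderate and severe events may be somewhat higher.

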16.4.2 Relatedness

The investigator will use the following definitions to assess the relationship of the AE to the investigational medical device:

Not related - The cause of the AE is known and the event is not related to the investigational medical device.

Possibly related - There is a reasonable possibility that the event may have been caused by the investigational medical device.

The AE has a timely relationship to the study procedure(s); however, follows no known pattern of response, and an alternative cause seems more likely or there is significant uncertainty about the cause of the event.

Probably related - It is likely that the event was caused by the investigational medical device.

The AE has a timely relationship to the study procedure(s) and follows a known pattern of response; a potential alternative cause, however, may explain the event.

Related - A related event has a strong temporal relationship and an alternative cause is unlikely.

16.4.3 **Outcome**

The clinical outcome of the AE or SAE will be characterized as follows:

Death - The SAE CRF must be completed for this outcome (see 16.5 Expedited Reporting of Serious Adverse Events).

Recovered without sequelae - The patient returned to baseline status

Ongoing - Patient did not recover and symptoms continue

Recovered with sequelae - The patient has recovered but with clinical sequelae from the event

Unknown - The patient outcome is unknown

Doc No: 220CLD

Rev: 03 Date: August 26, 2016

Page 53 of 93

16.4.4 Treatment or Action taken

The treatment or action taken after the occurrence of an AE or SAE will be reported as: Interventional Treatment - Surgical, percutaneous or other procedure Medical Treatment - Medication frequency of administration reduction/interruption or discontinuation, or medication initiated for event

None - No action is taken

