12. STUDY OBJECTIVE

The objectives are to assess the ease of use, tolerability, safety and efficacy of a new frequency of Vibrant Capsule administration: one per day for 2 days, followed by one day without (14 capsules in 3 weeks).

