17.8.4 Disposition of Subjects

Treatment tolerability will be presented, the number and percent of subjects who fail to complete the study and the number and percent of subjects who fail to complete the study because of Adverse Events will be presented. Time to withdrawal will also be assessed and presented by Kaplan-Meier.

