28. SUBJECT / STUDY DISCONTINUATION

Subjects should be removed from the study whenever considered necessary for their welfare or when the subject expresses a desire to withdraw from the study. Noncompliance with the protocol, the occurrence of a Serious Adverse Event or any medical condition that, in the opinion of the investigator, warrants discontinuation from the study for the safety of the subject, may necessitate discontinuing a subject. If a subject is discontinued, the reason must be entered on the case report form and signed by the investigator. In case of any questionable situation, the study monitor or Vibrant Ltd. personnel should be consulted. When a subject is removed from the study as a result of Serious Adverse Event, a final physical examination must be performed. Subjects removed from the study because of an adverse event will be followed-up until the adverse event has been resolved.

In the case that the occurrence of adverse events is greater than anticipated, the clinical investigation will be suspended; in such a case, a safety committee will be arranged to decide if the study could be continued. The Ethics Committee will be notified and the results of the safety committee discussions will be brought for the EC review and decision.

Doc No: 220CLD

Rev: 03 Date: August 26, 2016

Page 64 of 93

Early termination could be a result of:

1. Withdrawal of informed consent by the subject.

- 2. Patients who after inclusion develop medical diseases which may affect the function and interpretation of study results.
- 3. Serious protocol deviation.
- 4. Non-compliance with medical device administration or study procedures as determined by the sponsor.
- 5. Change in subject's condition.
- 6. Patient is Lost to follow-up.
- 7. Confirmed pregnancy.
- 8. Regulatory authorities stop the trial.

During the study, patients exiting the trial will be replaced with new patients, in order to have 120 patients at the end of the trial.

Vibrant Ltd., reserves the right to discontinue any study for administrative reasons at any time, such as, but not limited to a decision to discontinue further clinical investigation with the device, improper conduct of the study by the investigator, inability to obtain the number of subjects required by the protocol, etc. Reimbursements for reasonable expenses will be made if such an action is necessary.

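### The adverse-event action field has no code for a change in capsule use, so event-driven skipping or reduction in patients who stay in the study is neither directly recorded nor tabulated

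*Combined protocol and SAP*

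**What the plan says.** Section 16.4 requires a fixed description of every event: "All AEs will be characterized by the following criteria", followed by severity, relatedness, outcome and treatment or action taken. Section 16.4.4 then offers three actions:

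- Interventional Treatment, which means an operation or some other procedure
- Medical Treatment, which is defined as "Medication frequency of administration reduction/interruption or discontinuation, or medication initiated for event"
- a third entry for events that led to no action

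Section 12 makes the administration schedule the subject of the study: "The objectives are to assess the ease of use, tolerability, safety and efficacy of a new frequency of Vibrant Capsule administration". Section 17.3.1 has ease of use, tolerability and safety assessed at the interim, and one decision open under section 17.3.2 is "Modify the frequency of use and/or the device's usability".

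For tolerability, section 17.8.4 specifies non-completion overall, non-completion for adverse events ("the number and percent of subjects who fail to complete the study because of Adverse Events will be presented") and a Kaplan-Meier display of time to withdrawal. Section 17.8.7 breaks adverse events down by seriousness, severity and relatedness. Action taken is not among its breakdowns.

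**The concern.** In a study of how often a capsule can be taken, an adverse event after which the patient takes fewer capsules is direct evidence about tolerability. The action field is where that link would normally be recorded. Here it combines two different responses: changing administration, and giving a drug for the symptom. Someone reading the field alone cannot tell which occurred.

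The interim decision and the final account of tolerability are both affected. The specified tolerability measures concern leaving the study. A patient who finds the schedule hard to tolerate, omits capsules and still attends the last visit counts as a completer in all of them.

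**Working it through.** No formula applies, because the plan states no figure for this point. The check is to follow each kind of event through the records that the plan specifies.

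**Step 1: reading the category.** The word medication in section 16.4.4 can be read in two ways. The protocol uses frequency of administration for the capsule schedule in the synopsis and in sections 12 and 15.1, so the more natural reading includes the capsule. Capsule changes and new drugs then share a code. If medication means drugs only, no code exists for an action on the capsule. A capsule-specific code is absent on either reading.

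**Step 2: tracing events (natural reading).**

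| What follows the event | Action code (16.4.4) | Other record | Planned table |
|---|---|---|---|
| Drug given, capsules unchanged | Medical Treatment | Drug with date and reason (15.12) | None by action |
| Capsules skipped or reduced, patient stays | Medical Treatment | Gap in activation log (15.1); returned capsules (15.9, 15.11); possibly a deviation form (15.16) | None |
| Capsules stopped, patient stays | Medical Treatment | As above | None |
| Patient leaves the study | Medical Treatment, if capsules stop | Reason on the CRF (28) | Yes (17.8.4) |

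The first three rows share a code. Only the last has a planned count.

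**Step 3: what the other records show.** Two capsule days in every three gives 7 × 2 = 14 capsules in 21 days and 14 × 2 = 28 in 42 days, which matches sections 12 and 15.1. The activation log can therefore be compared with an expected 28, and missed capsules can be counted. The log holds times but no reasons: a gap may reflect forgetting, a faulty unit or an adverse event. The calls in section 15.9 cover compliance and adverse events together, but only the date and time of the call are specified for eCRF entry. The reason field in section 15.12 applies to drugs taken. The reason in section 28 applies to subjects who are discontinued. None of these is specified to link a named event to a capsule change in a continuing patient.

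**Step 4: the interim.** The synopsis and section 15.1 trigger it when 20 patients have completed and are evaluable; section 17.3 says approximately 20 who complete six weeks. The documents do not say whether patients who have withdrawn by then are included. If the interim set is the completers alone, non-completion in it is zero by construction, and the section 17.8.4 measures add nothing to the frequency decision. Event-driven capsule changes among those completers would then carry much of the remaining information on tolerability.

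**The case against.** The strongest reply is that the plan collects much of this elsewhere. Section 15.1 puts capsule usage on the eCRF together with adverse events occurring during use, and has the base unit send activation times automatically. Unused capsules come back at day 21 and at termination. Drugs are recorded with reasons. The protocol sets one fixed sequence, so an individual cut in frequency would be a deviation with its own form. Section 28 adds: "If a subject is discontinued, the reason must be entered on the case report form and signed by the investigator". Section 17.8.4 also promises, in general terms, that tolerability will be presented. The AE page of the eCRF is not in the documents and may offer finer options. Finally, section 15.1 calls this a pilot, the analyses are mainly descriptive, and neither the primary endpoint nor the planned AE tables depend on action taken.

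Most of this stands, and it limits the point. A reader might infer from section 16.4.4 that event-driven capsule changes cannot be identified at all, or that only patients who leave the study can be counted. The documents do not support either inference: withdrawals are captured with reasons, missed capsules can be counted, and some cases could be worked out by matching dates across records.

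The reply does not supply the link itself. Matching dates shows that an event and a gap coincided, not that one led to the other, and no such matching is planned. Section 28 also lists non-compliance with device administration as a ground for early termination, so event-driven skipping could be filed as non-compliance.

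**Conclusion.** The point holds in a limited form. Section 16.4.4 has no capsule-specific action code, and event-driven skipping, reduction or stopping in patients who remain in the study is neither coded directly at event level nor tabulated. It could be inferred only in part from other records. Withdrawals because of adverse events are properly covered.

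The size cannot be given as a number. The documents state no rate of event-driven capsule changes and plan no table by action taken. A reader tempted to attach a percentage range to the ambiguity would have to invent the inputs and ignore the activation and concomitant-medication records.

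In practical terms, one stated objective and the interim choice about frequency lose direct evidence, while the primary efficacy result and the planned safety tables are unaffected. This is a worthwhile improvement, not a threat to validity. The conclusion assumes that the eCRF follows the three categories as printed. If the page already separates capsule actions, only the missing table remains. The remark about zero non-completion at the interim also assumes that the interim set is completers only.

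**What to change.** Replace the single field in section 16.4.4 with two, completed independently for each event:

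- (a) action with the capsule: none / capsule(s) skipped / frequency reduced / stopped
- (b) treatment of the event: none / medication / procedure

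In section 17.8.7 and in the interim report (section 17.3.1), add the number and percent of subjects with at least one adverse event leading to each action in (a). The Full Analysis Set, which section 17.7.3 names as the main set for safety, is the natural denominator for the final table. At the interim, state which subjects are counted.

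Field (a) records what happened. It neither permits nor recommends any change in capsule use. The cost is one extra field on the AE eCRF page and one table, with no added visit or test for patients. It should be in place before the first capsule is given, because the reason for a missed capsule is hard to recover later.
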